600 mg of gabapentin was selected as a well-tolerated intermediate dosage with benefit proven in prior perioperative pain studies. The window of 1-2 hours is consistent with preoperative dosing in other studies and can allow for its co-administration with misoprostol, and allows for some variability that is practical with a busy clinic.

Study Procedures:

All recruitment, screening and enrollment questions will be asked by trained study staff in a private room.

Recruitment:

We will be recruiting a total of 96 women, with equal allocation to the invention group and placebo. The proposed research will take place at Duke Ryan Clinic, at the Duke gynecology outpatient clinic. Women who attend Duke for a uterine aspiration will have their preoperative evaluation and over the phone counseling. During this call, the clinical provider will introduce the study to the patient to determine interest in participating in the study. All patients are scheduled and given standardized pre-procedure counseling by our clinic coordinator. If the patient is interested in possible participation, study personnel will be notified. The study team will then contact the patient to provide them with information about the study. A standard recruitment script will be employed (Appendix A).

Screening and consent:

For individuals who are interested in participating, we will screen for eligibility using an eligibility checklist (Appendix A). Those eligible after screening will review the informed consent and sign consent forms prior to the final clinical preoperative review. Patient contact information will be collected at this time. After the nurse reviews the medical chart, randomization will occur and intervention will be received.

Randomization, Allocation Method and Blinding:

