We will collect baseline demographics, medical history (gravidity, parity, prior abortions (medical and surgical), gestational age, drug and alcohol use, psychiatric or sexual assault history), medications used at home and given at the clinic preoperatively, indication for procedure (personal/social, fetal or maternal health)).

Study Size and Power:

We will enroll a total of 96 women. Assuming a standard deviation of 26 mm on the 100-mm visual analog scale (VAS), based on prior studies, this will provide us with an 80% power, using a p-value of 0.05, to detect a 15 point difference in pain among all participants. A difference of 15-20 mm has been assessed to be clinically meaningful in prior studies. Given that our primary outcome will be measured immediately after the procedure, our loss to follow-up will be minimal. A 100-mm pain visual analog scale has been shown to be useful for the evaluation of pain in prior pain abortion research [5, 6] with a mean standard deviation in previous studies of approximately 26 mm [5]. We are assuming no loss-to-follow-up as our primary outcome will be measured at the time of the procedure.

Data Management and Analysis

Data Management:

Prior to study initiation, a database will be developed using a web-based password-protected relational database (REDCap). All data will be collected will be recorded on clinical research forms (CRFs) and entered into the database at the end of each day. All CRF source documents will be filed and stored for future reference. See monitoring and oversight section below for further details on procedures and protections.

Analytic Plan:

We will compare groups on the primary continuous outcome measure (pain score on 11-point VAS) using T-tests. Chi-square and T-tests will be used to evaluate secondary outcomes for categorical and continuous variables, respectively. Baseline characteristics will be evaluated for potential interaction or confounding with primary and secondary outcomes.

Upon study completion at each site for the prospective meta-analysis, data from each site will contribute to the final meta-analysis using criteria outlined in the Cochrane Handbook for Systematic Reviews of Interventions. Site RCT publications will mention contribution to this PMA. Subgroup analyses will address gabapentin adjunct to local anesthesia and moderate sedation, as well as by specified population characteristics and gestational age.

Ethical Concerns

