The study will not commence until the study protocol has been reviewed and approved by the Duke University institutional review board (IRB).

Potential risks:

Risk of medication: Gabapentin has been used in several other clinical settings and is associated with few side effects, thus the risks associated with its use as an adjunct to abortion perioperative

pain regimens in minimal. As this is a low-cost intervention that has promise for improving pain, the potential for risk is balanced by the potential benefit. Side effects and adverse effects will be carefully tracked and monitored during the study. Documented side effects of gabapentin include: dizziness, somnolence, fatigue, ataxia, peripheral edema, nystagmus, nausea and vomiting, asthenia, headache, weight gain, amblyopia, however most of these are associated with chronic usage. Other rare side effects include: DRESS (drug reaction with eosinophilia and systemic symptoms), multi-organ hypersensitivity, withdrawal seizures (if given for epilepsy), suicidal behavior and ideation, neuropsychiatric reactions in pediatric patients (3-12 yo), and sudden death.

Sensitive information: The risks involved in study participation are those related to providing personal information about sensitive topics. Participants' privacy and the confidentiality of data will be protected through training of study staff, conducting all interviewing and physical examinations in private, storing study materials in a locked room, and securing computer files that include identifiers. Only the study identification number will identify participant research records. Linkages between the ID number and participants' identifying information will be maintained in a computer database that is password protected and only accessible to study staff. These linkages will be destroyed after completion of study activities. We will ensure that study staff is thoroughly trained to not to disclose any information about the study or the participant's attendance at the clinic to any individual other than the study participant. Breaches of confidentiality are possible, though safeguards are in place to protect the confidentiality of participants. Thus, the potential for experiencing an adverse event is minimal.

Protection against risks

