An adverse event (AE) is defined as any health-related reaction, effect, toxicity or abnormal laboratory result that a study participant experiences during the course of the study, irrespective of relationship to the study intervention. This includes changes in a participant's condition that have or could have a deleterious effect on a participant's health or well-being. A serious adverse event (SAE) is defined as any experience that is fatal or life-threatening, requires

in-patient hospitalization or prolongation of an existing hospitalization, or results in a persistent or significant disability or incapacity.

This study uses an additional medication for pain control in the setting of outpatient abortion. These activities are not anticipated to be associated with any deleterious impact on participants' health or well-being beyond the risks associated with the abortion procedure. AEs will be managed according to good clinical practice and the judgment of the on-site physician. All clinical and laboratory AEs will be followed-up closely by study staff. Any SAEs will be expeditiously reported to the principal investigators, via a designated SAE form. Notification and submission of SAE forms should occur within 48 hours of the site awareness of the SAE. The PI will then make the final independent judgment as to the severity, relatedness, and anticipated or unanticipated nature of the SAE and finalize the Human Subjects Adverse Event Report Form. If the event is determined to be serious, unanticipated, and the relationship is anything other than probably or definitely not related, then the PI will report the event within 48 hours and submit the required forms to the IRB at Duke. Thus, all anticipated SAEs that are at least possibly related to study intervention and all deaths that are at least possibly related to study intervention will be submitted to the Duke IRB.

The study may be discontinued at any time by an IRB at a participating institution or the Office for Human Research Protection. We will additionally have a medical monitor to review any adverse event and periodically review side effects to see if there are an increased number of events than anticipated by routine clinical care. If any suspicion for increased risk exists, study allocation may be revealed for a preliminary analysis and if related to the study intervention, the study could be prematurely ended.

Data Monitoring Committee/Study Termination

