ANXIOUS**4. Make a hash mark on the line to indicate how much nausea you are currently experiencing.**NO
NAUSEA _____WORST NAUSEA
I HAVE EVER HAD5. Have you vomited since you had your procedure? ₀ NO ₁ YES

SIDE EFFECTS: Do you have any of the following?

Dizziness	 ₀ NO  ₁ YES, mild  ₂ YES, moderate  ₃ YES, severe
Ataxia (lack of muscle control)	 ₀ NO  ₁ YES, mild  ₂ YES, moderate  ₃ YES, severe
Somnolence (sleepiness or drowsiness)	 ₀ NO  ₁ YES, mild  ₂ YES, moderate  ₃ YES, severe
Asthenia (weakness, lack of energy)	 ₀ NO  ₁ YES, mild  ₂ YES, moderate  ₃ YES, severe
Headache	 ₀ NO  ₁ YES, mild  ₂ YES, moderate  ₃ YES, severe
Amblyopia (vision in one eye reduced/lazy eye)	 ₀ NO  ₁ YES, mild  ₂ YES, moderate  ₃ YES, severe

Post- anesthetic alдрete recovery score : modified Criteria	Points
Oxygenation	
SpO ₂ > 92% on room air	2
SpO ₂ > 90% on oxygen	1
SpO ₂ < 90% on oxygen	0
Respiration	
Breathes deeply and coughs freely	2
Dyspneic, shallow or limited breathing	1
Apnea	0
Circulation	
BP +/- 20% of normal	2
BP +/- 20-50% of normal	1
BP > 50% of normal	0
Consciousness	
Fully awake	2
Arousable on calling	1
Not responsive	0
Activity	
Moves all extremities	2
Moves two extremities	1
No movement	0

30-Minute Post Op Assessment

Time: ____ : ____ AM/PM

1. Make a hash mark on the line to indicate the worst pain you have felt up to this point today.NO
PAIN _____WORST PAIN
IN MY LIFE**2. Make a hash mark on the line to indicate how much pain you are currently in.**NO
PAIN _____WORST PAIN
IN MY LIFE**3. Make a hash mark on the line to indicate how much anxiety you are currently experiencing.**NO
ANXIETY _____EXTREMELY
ANXIOUS**4. Make a hash mark on the line to indicate how much nausea you are currently experiencing.**NO
NAUSEA _____WORST NAUSEA
I HAVE EVER HAD

4. Have you vomited since you had your procedure?

 ₀ NO ₁ YES

Discharge Assessment

Time: ____ : ____ AM/PM

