1. Make a hash mark on the line to indicate the worst pain you have felt up to this point today.

NO
PAIN _____

WORST PAIN
IN MY LIFE

2. Make a hash mark on the line to indicate how much pain you are currently in.

NO
PAIN _____

WORST PAIN
IN MY LIFE

3. Make a hash mark on the line to indicate how much anxiety you are currently experiencing.

NO
ANXIETY _____

EXTREMELY
ANXIOUS

4. Make a hash mark on the line to indicate how much nausea you are currently experiencing.

NO
NAUSEA _____

WORST NAUSEA
I HAVE EVER HAD

5. Have you vomited since you had your procedure? ₀ NO ₁ YES

Post- anesthetic Aldrete recovery score Modified Criteria [2]	Points
Oxygenation SpO ₂ > 92% on room air SpO ₂ > 90% on oxygen SpO ₂ < 90% on oxygen	2 1 0
Respiration Breathes deeply and coughs freely Dyspneic, shallow or limited breathing Apnea	2 1 0
Circulation BP +/- 20% of normal BP +/- 20-50% of normal BP > 50% of normal	2 1 0
Consciousness Fully awake Arousable on calling Not responsive	2 1 0
Activity Moves all extremities Moves two extremities No movement	2 1 0

24 hours post-procedure measures

Time: _____ AM/PM

Did you fill any pain medication prescription? ₀ NO ₁ YES

Have you taken any medication since you left the clinic for pain, nausea, vomiting or any other medication

Have you vomited since you left the clinic? NO YES, number of times _____

Overall satisfaction with experience 0-10 scale (0 = very dissatisfied; 10 = very satisfied): _____

Quality of Recovery Survey[3]

Part A

	How have you been feeling in the last 24 hours? (0 to 10, where 0 = none of the time [poor] and 10 = all of the time [excellent])	0-10
1	Able to breathe easily	
2	Been able to enjoy food	
3	Feeling rested	
4	Have had a good sleep	
5	Able to look after personal toilet and hygiene unaided	
6	Able to communicate with family and friends	
7	Getting support from hospital doctors and nurses	
8	Able to return to work or usual home activities	
9	Feeling comfortable and in control	
10	Having a feeling of general well-being	

Part B

	Have you had any of the following in the last 24 hours? (0 to 10, where 10= none of the time [excellent] and 0 = all of the time [poor])	0-10
1	Moderate pain	
2	Severe pain	
3	Nausea or vomiting	

4	Feeling worried or anxious	
5	Feeling sad or depressed	

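### The draft forms do not systematically ask about adverse events after discharge, although the protocol counts any health event and treats hospital admission as serious

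*Combined protocol and SAP*

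**What the plan says.** The Secondary Aims of the combined protocol and SAP include evaluating side effects and adverse events of gabapentin. The Adverse events section defines an adverse event as "any health-related reaction, effect, toxicity or abnormal laboratory result that a study participant experiences during the course of the study", whatever its cause, and lists in-patient hospitalization among the criteria for a serious event. On reporting, it says "Notification and submission of SAE forms should occur within 48 hours of the site awareness of the SAE". Under Potential risks the protocol promises: "Side effects and adverse effects will be carefully tracked and monitored during the study".

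Secondary Outcomes describes a side-effect checklist before discharge and a contact on post-operative day 1 that is to cover pain, nausea, vomiting, side effects and satisfaction. Follow-up describes one telephone call at about 24 hours. No later contact is planned.

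In the Draft Questionnaire, the checklist appears once, in the 10-Minute Post Op Assessment, under "SIDE EFFECTS: Do you have any of the following". It lists dizziness, ataxia, somnolence, asthenia, headache and amblyopia. The form for the call (24 hours post-procedure measures) asks about a filled pain prescription, medication taken, vomiting ("Have you vomited since you left the clinic"), overall satisfaction and the 15 items of the recovery survey.

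**The concern.** The definition is broad but the questions are narrow. A woman who called a clinic, attended an emergency department or was admitted overnight could answer every item on the last form without being asked about it. The same holds for a new symptom outside the six on the checklist.

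The medical monitor is to judge whether events exceed what routine care would produce, and the DMC is to review safety data. Both depend on what the site comes to know. If knowledge of post-discharge events is incidental, a low count says less about safety than it appears to, and the secondary aim on adverse events is only partly served.

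**Working it through.** **1. The plan's own figure.** Study Size and Power states "We will enroll a total of 96 women", and Recruitment says "with equal allocation to the invention group and placebo". With SD 26 mm, difference 15 mm, two-sided alpha 0.05 (the plan does not state sidedness) and 80% power, n per arm = 2(1.96 + 0.8416)² × 26²/15² = 47.2, rounded up to 48, so 96 in total. Power at 48 per arm is 80.7% by the normal approximation and 79.9% for the t-test. The figure reproduces. The present point does not depend on it, except that 48 and 96 are the denominators for safety counts.

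**2. Commitments set against the day-1 form.**

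| Commitment | Where stated | Item on the 24-hour form |
|---|---|---|
| Side effects assessed on day 1 | Secondary Outcomes | None; the checklist is only in the 10-minute assessment |
| Any health event is an adverse event | Adverse events | No open question on new health problems |
| Hospitalization is a serious event | Adverse events | No question on admission or unscheduled care |
| Vomiting | Secondary Outcomes | Asked directly |
| Medication use at home | Secondary Outcomes | Asked directly |

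**3. Other forms.** The checklist has no *other* line. Peripheral edema, nystagmus and hypersensitivity are named among the risks of the drug but have no field on it. The chart abstraction has one free-text field for complications, limited to the procedure. Secondary Outcomes provides for abstraction of medications from the clinical record but describes no search for post-discharge events.

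**4. Timing.** The drug is given 1-2 hours before the procedure, with a stated 2-hour time to peak and a 5-7 hour half-life. A checklist 10 minutes after the procedure therefore leaves much of the exposure to the day-1 call.

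**5. Routes by which the site could still learn of an event.** These are the medication question, recovery items on breathing, severe pain and support from hospital staff, interviewers trained to recognize complications (Protection against risks), the woman's own report, and ordinary clinical care. None is a direct question about events.

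**6. Scale, on assumed inputs.** The documents give neither a post-discharge serious-event rate p nor a capture proportion s. The chance of recording at least one event is 1 − (1 − ps)^n. With n = 96:

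| Assumed p | s = 1 | s = 0.5 | s = 0.25 |
|---|---|---|---|
| 0.5% | 38% | 21% | 11% |
| 1% | 62% | 38% | 21% |
| 2% | 86% | 62% | 38% |

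The one-sided 95% upper bound on the true rate after zero recorded events is (1 − 0.05^(1/n))/s. For 96 women it is 3.1% with full capture and 0.0307/0.5 = 6.1% with half. For one arm of 48 it is 6.1% with full capture and 0.0605/0.5 = 12.1% with half.

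**The case against.** The strongest reply is that the questionnaire is not the whole safety system. The Adverse events section sets up physician judgment, staff follow-up, a designated form for serious events, a report form and a medical monitor. An event seen in clinic can enter there without a checklist line. Both recovery scores also record oxygenation, respiration, circulation and consciousness. A reader might infer that unlisted events cannot be recorded at all, or that serious events surface only if a woman volunteers them. The documents support neither: that process exists, interviewers are to be trained, and several day-1 items could prompt disclosure. What remains is that the described forms and process act on events already known, and no step finds them after discharge.

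The questionnaire is labelled a draft, and operational detail is left to an operations manual that is not reproduced, nor is the serious-event form. The consent text, which may tell women how to report problems, was not available for this check. No claim is made about any of these.

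Most of the listed side effects are said to go with chronic use, so edema or nystagmus after one dose is a weak example. Unscheduled care and admission are the better ones.

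Finally, small numbers limit the safety conclusions in any case. Even with full capture, zero events in 48 women leaves an upper bound of 6.1%. That is correct, and incomplete capture widens it further.

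**Conclusion.** The point holds as a gap between what the protocol commits to and what its draft forms ask. Side effects are promised on day 1 but absent from that form, and neither an open health question nor a care-use question is put to the participant at the last contact. Post-discharge adverse-event and serious-event counts would probably be incomplete.

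The size of the shortfall cannot be derived from the documents. The rates and capture proportions in the working are assumptions that show scale only. A reader might also infer a biased comparison between arms. The documents give no reason for that: participants and assessors are blinded, so under-collection should affect both arms alike, and the harm is to absolute counts and to any reassurance drawn from few events. The primary outcome and its analysis are untouched. This is a cheap improvement worth making before the form is finalised, not a flaw that undermines the trial.

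**What to change.** Three changes to the Draft Questionnaire:

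- Add a line to the 10-minute checklist: *Other new symptom or health problem since the study pill (describe; mild, moderate or severe)*.
- Make the 24-hour form match Secondary Outcomes by adding the same checklist, including that line, with the stem reworded to cover the time since leaving the clinic.
- Add to the 24-hour form: *Have you called or visited a clinic, emergency department or hospital, or been admitted, since you left (reason, date)?*

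Send any positive answer to the existing adverse-event and serious-event process, and state in the Analytic Plan that these events will be tabulated by arm. The cost is a few form lines, about a minute of a call already planned, and more minor events to log. Treatment, sample size and primary analysis do not change.

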Pain control during and after abortion is a Society of Family Planning priority. Pain management regimens for surgical abortion can rely on local anesthetic, oral analgesics, moderate sedation, deep sedation, or a combination of approaches. While several recent studies have attempted to reduce pain with adding supplemental medications or therapies, such as nonsteroidal anti-inflammatory drugs, narcotics, anxiolytics, misoprostol, nitrous oxide, music, most studies have failed to improve pain scores. As optimal pain management has not been established, many women continuing to report moderate to severe pain during and after the procedure [1].

We propose a novel regimen of oral gabapentin administered prior to usual pain management regimens for surgical abortion. Gabapentin is used to treat neuropathic and chronic pain. Mechanism of action may include calcium channel blockade and modulation of nociceptive neurotransmitters. Clinical trials support use of perioperative gabapentin to reduce post-surgical pain in a variety of clinical settings[2]. Gabapentin is well-tolerated and inexpensive, with mild, if any, side effects. [3] In a systematic review of 22 randomized controlled trials (RCT) of multiple surgical procedures including ambulatory nasal surgery, orthopedic procedures and laparotomy, a single preoperative dose of gabapentin significantly reduced 24-hour opioid consumption[3]. Perioperative gabapentin before hysterectomy showed reduced pain scores, nausea and vomiting [4, 5] A randomized trial in the setting of cesarean showed improved pain scores and decreased pain requirements with a 600 mg dose of preoperative gabapentin [5]. Its use in the setting of abortion has never been evaluated.

We hypothesize that adding gabapentin preoperatively to current pain management regimens will reduce pain associated with surgical abortion. Additionally, we hypothesize that preoperative gabapentin will reduce perioperative nausea, vomiting and anxiety with few adverse effects.

Primary Aim: To evaluate the impact of adjunctive preoperative gabapentin on perioperative pain during uterine aspiration <15 weeks of gestation for abortion and pregnancy loss management compared to usual pain control regimens

Secondary Aims

- To evaluate the impact of preoperative gabapentin on:
 - perioperative nausea and vomiting
 - preoperative anxiety
 - use of pain medications and anti-emetics post-operatively

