Randomization to study method will occur after completion of all intake forms and consent, immediately before the pill is to be taken, thus reducing the possibility of withdrawal after randomization. Primary outcome measures and most secondary outcome measures will be assessed immediately before, during or after the abortion procedure, thus any loss to follow-up will be limited to those who consent to, but change their mind while waiting for their procedure. Based on current clinical practice at this clinic, withdrawal after consent is extremely rare. Our secondary outcomes assessed post-operatively after discharge will be collected via the phone. We will maximize completion of these assessments through the following steps: participants will be told beforehand about the telephone contact following the procedure, a cellular telephone number will be collected and tested at the clinic, a secondary phone number and email will be collected as a backup, participants will be given a contact number for the study coordinator should they have any challenges with receiving a phone calls, and participants will receive an additional \$10 sent to their gift-card following the completion of their phone assessment.

Data Collection/Outcome measurements:

Outcome measures and baseline variables are described in Table 1.

Primary study outcome

Our primary outcome measure will be pain score using an 100-mm visual analog scale (VAS) measured 5 minutes after removal of the speculum.

Secondary Outcomes:

We will also be measuring pain on the 100-mm VAS preoperatively immediately prior to the procedure, after the procedure, 10 minutes and 30 minutes following the procedure and at discharge. Nausea, using a VAS, and vomiting will be assessed preoperatively immediately prior to the procedure and post operatively at 10 minutes, 30 minutes and at discharge. Anxiety prior to the procedure will be measured using the preoperative state trait anxiety inventory. Side effects will be assessed using a checklist prior to discharge. We will also be contacting participants on post-operative day 1 to assess pain, nausea, vomiting, side effects and general satisfaction with the procedure (on a 5-point scale). The quantity and type of medications used perioperatively and post-operatively including medications used at home in the 24 hours post-operatively will be abstracted from the clinical record and assessed on the phone.

Baseline Characteristics and covariates:

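### The day-1 call is meant to assess nausea apart from vomiting, but its form rates nausea only in a pooled item, so day-1 nausea alone has no clean randomised comparison

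*Combined protocol and SAP*

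**What the plan says.** Nausea is part of the trial's stated purpose. The secondary aims include the effect of gabapentin on "perioperative nausea and vomiting", and the introduction states that "we hypothesize that preoperative gabapentin will reduce perioperative nausea, vomiting and anxiety with few adverse effects".

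For the clinic stay, the Secondary Outcomes section names an instrument: "Nausea, using a VAS, and vomiting will be assessed preoperatively immediately prior to the procedure and post operatively at 10 minutes", then at 30 minutes and at discharge. For the next day it says: "We will also be contacting participants on post-operative day 1 to assess pain, nausea, vomiting, side effects and general satisfaction with the procedure". Nausea and vomiting are separate entries in that list, and no instrument is named for day-1 nausea.

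The Draft Questionnaire carries a nausea-only line on the preoperative, 5-minute, 10-minute, 30-minute and discharge forms. The postoperative wording is "Make a hash mark on the line to indicate how much nausea you are currently experiencing". The immediate post-operative form has a pain line only.

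The 24-hour form asks about filling a pain prescription, medication taken since leaving, vomiting since leaving (with a count), overall satisfaction, and the Quality of Recovery Survey. Part B item 3 of that survey reads "Nausea or vomiting". It is scored from 10 (none of the time) to 0 (all of the time) over the last 24 hours.

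**The concern.** The outcome list promises day-1 nausea as an outcome in its own right, and the form does not collect it that way. The pooled item gives one number for two symptoms. A woman with lasting nausea who never vomited and a woman who vomited repeatedly can return the same score. The item also records how much of the time symptoms were present, not how bad the nausea was.

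If the call is run on this form, the trial will have day-1 vomiting by arm and a combined nausea-and-vomiting score by arm, but no day-1 nausea result by arm that stands alone. A question not asked on the call cannot be recovered afterwards.

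**Working it through.** This is mainly a comparison of the outcome list with the form. The documents give no expected value, SD or power for nausea. The only sample-size figure is for the pain score: 15 mm, SD 26 mm, 80% power and p = 0.05 (taken as two-sided) give 48 per arm, 96 in total, as stated. Nothing here depends on it.

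**Step 1: outcome list against form, day 1.**

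| Symptom | Listed for day 1 | Own item on the 24-hour form |
|---|---|---|
| Vomiting | Yes | Yes: yes/no with number of times, since leaving the clinic |
| Nausea | Yes, separately | No: only the pooled recovery-survey item |

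The medication question mentions nausea, but it records treatment taken for pain, nausea, vomiting or any other reason together. It is not a nausea rating.

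**Step 2: is there a rule for extracting nausea?** The Analytic Plan gives t-tests for continuous and chi-square tests for categorical secondary outcomes. It has no rule for deriving nausea from the pooled score.

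**Step 3: what can be recovered from the two items together?** Let C be the share of an arm scoring below 10 on the pooled item and V the share who vomited, all of them within C. The share with any nausea then lies between C − V and C. The documents give no rates, so these values are assumptions:

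- C = 0.30, V = 0.05: 0.30 − 0.05 = 0.25, so nausea lies in 0.25–0.30.
- C = 0.40, V = 0.20: 0.40 − 0.20 = 0.20, so nausea lies in 0.20–0.40.

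If the first line were the gabapentin arm and the second the placebo arm, the pooled item would differ by 0.30 − 0.40 = −0.10. The difference in nausea alone could lie anywhere from 0.25 − 0.40 = −0.15 to 0.30 − 0.20 = +0.10. These are worst-case limits: the lower end in each arm supposes that nobody who vomited was nauseated. If everyone who vomited is assumed to have been nauseated, the any-nausea share is simply C. Even then the 0–10 score of a woman who vomited cannot be divided between the two symptoms.

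**Step 4: would restricting to women who did not vomit solve it?** In those women a score below 10 points to nausea. But vomiting happens after randomisation and the trial hypothesises that gabapentin reduces it, so the non-vomiters in the two arms need not be comparable.

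**The case against.** The strongest reply is that the gap is small and may already be closed. The questionnaire is headed as a draft, and Table 1, which the protocol cites for its outcome measures, is not in the supplied text. No section names the pooled item as the day-1 nausea outcome, so the plan cannot be said to have chosen a bad measure. The call does carry information on nausea, and the bounds above are narrow when vomiting is uncommon. The aim concerns perioperative nausea, which the clinic lines address directly. The day-1 sentence requires neither a severity scale nor a window that starts at discharge.

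Most of this stands and limits the point. It does not remove the mismatch: nausea is listed separately, the form does not ask about it separately, and nothing supplied adds the question.

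A reader might infer more than the documents support:

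- *That day-1 nausea cannot be analysed at all.* It can be partly inferred; what is missing is a clean randomised comparison of nausea on its own.
- *That vomiting is counted twice.* That would follow only if the pooled item were the designated nausea outcome, which is nowhere stated.
- *That most of any drug effect on nausea falls after discharge.* The protocol gives a half-life of 5–7 hours, but also a 2-hour time to peak with dosing 1–2 hours beforehand, and no discharge time.
- *That a specific loss of power follows.* With no nausea SD or effect, and no correlation between the pooled item and nausea, any such figure would be borrowed from pain and assumed. The drug is also hypothesised to reduce vomiting, so a pooled item need not lose power.
- *That the call breaks a uniform clinic series.* The immediate post-operative form has no nausea line, and the protocol states a 100-mm length for pain but not for nausea.

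**Conclusion.** The point holds in a limited form. The protocol lists nausea apart from vomiting for the day-1 call, and the draft form provides only a pooled frequency item, so nausea alone cannot be compared between the randomised arms at that time without an untestable assumption or selection on a post-randomisation event.

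Severity is minor: the loss is confined to this one secondary outcome at this one time point. The conclusion rests on the supplied text being complete on this matter; a nausea item in Table 1 or in a final version of the form would close it. The size of the ambiguity depends on how many women vomit after the procedure, which the documents do not give.

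**What to change.** Add one verbal 0–10 question to the 24-hour call: worst nausea since leaving the clinic, anchored at no nausea and the worst nausea ever had. Name it in the Secondary Outcomes section as the day-1 nausea outcome. Keep the vomiting question and the recovery survey unchanged.

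Analyse the new item as a separate day-1 measure. A recalled worst rating given by telephone is not the same as a marked line for current nausea, so it should not be presented as a continuation of the clinic scale. Where possible, agree the wording with the other sites in the prospective meta-analysis.

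The cost is one extra question on a call already planned and one line in the outcome list. The small downside is that the item may not be poolable if the other sites do not ask it.
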